Study population:	Nulliparous women with a diagnosis of PCOS who are eligible for IVF (in vitro fertilization) treatment with freeze-only strategy (i.e. deferred embryo transfer). Nulliparous women who embark on elective oocyte

	
cryopreservation. Both groups will receive PPOS (progestin-primed ovarian stimulation).

In- and exclusion criteria:	
Inclusion criteria PCOS group :
 
 - Diagnosis of PCOS according to the 2004 Rotterdam criteria - Initiating their first cycle of IVF treatment (PPOS and freeze only protocol) - Nulliparous - ≥ 18 years - Willing to participate in the study - Understanding Dutch, French or English 
Exclusion criteria PCOS group :
 
 - Known inflammatory bowel disorder - Known major intestinal bowel disorder - Known systemic or auto-immune disorder with implication for the GI system - History of abdominal surgery (appendectomy and cholecystectomy allowed if >6 months earlier) - History of gastro-enteritis in the past 6 weeks - Previous IVF treatment cycles 
Inclusion criteria social freezing group:
 
 - Initiating their first ovarian stimulation protocol for elective oocyte cryopreservation (PPOS and freeze only protocol) - Nulliparous - ≥ 18 years - Willing to participate in the study - Understanding Dutch, French or English 
Exclusion criteria social freezing group:
 
 - Diagnosis of PCOS - Known inflammatory bowel disorder - Known major intestinal bowel disorder - Known systemic or auto-immune disorder with implication for the GI system - History of abdominal surgery (appendectomy and cholecystectomy allowed if >6 months earlier) - History of gastro-enteritis in the past 6 weeks
Factors of interest / Data to be collected:	
IBS diagnosis and symptom severity Gastrointestinal symptom severity Depression levels Anxiety levels
 
Factors to be collected before ovarian stimulation:
 
 • Demographics (length, weight) • The duration of infertility • Obstetrical history: GPA (Gravida, Para and abortus) • The ethnicity • For the study group: the type of PCOS 
Factors to be collected after oocyte pick-up:
 
 • The hormonal profile at start and end of ovarian stimulation • The number of follicles on the last ultrasound before pickup • The number of COC (Cumulus-oocyte complex) collected during pick-up

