10.3 Data collection from patient file

The patient file will be utilized to collect specific data for the purpose of this study. The following information will be gathered: age, the type of medication administered for ovarian stimulation, the hormonal profile, the number of follicles observed on the final ultrasound, and the number of oocytes retrieved during oocyte pick-up (OPU). This data will be obtained post-OPU.

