10.5 Statistical Considerations and Data Analysis

The primary objective of this study is to investigate whether fertility treatment is associated with changes in the **prevalence** and **severity** of Irritable Bowel Syndrome (IBS) symptoms. Specifically, the study aims to:

3. Assess whether the **proportion of participants meeting IBS diagnostic criteria** (based on ROME III and IV) differs **before and after fertility treatment**.
4. Evaluate whether there is a **statistically significant change in IBS symptom severity** as measured by the **IBS Symptom Severity Score (IBS-SSS)** before and after treatment.
5. Identify which **psychological and clinical factors** are associated with the presence or change in IBS symptoms in women undergoing fertility treatments, including those with **Polycystic Ovary Syndrome (PCOS)** and those undergoing **social oocyte freezing**.

Participants will either meet the criteria for IBS or not meet the criteria for IBS (based on the ROME III and IV criteria). This will correlate to a binary outcome: yes (1) or no (0) answer. This answer will be defined before and after the fertility treatment. A logistic regression model will be used to determine the chance of P(1) which is the chance of meeting the IBS criteria (yes answer). This regression model will be used for the PCOS group and the social freezing group. This model estimates the probability of an event occurring (meeting the IBS criteria) based on a given set of independent variables. The independent variables include GAD-7 score, PHQ-9 score, ethnicity, duration of the desire to have children, the number of follicles found on the US,...

These independent variables will be evaluated with the AIC (Akaike information criterion). AIC is used to compare different possible regression models and define which model is the best fit for the given data. If the AIC is lower, the data is a better fit. The regression model will be made with different independent variables and each time the AIC will be calculated. The model with the lowest AIC will be the final model.

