Participants will fill in the IBS-SSS and obtain a score between 0 and 500. The difference in score before and after the fertility treatment will be calculated. This score difference, which is a continuous outcome, will be used in a multiple linear regression model. This model estimates how several independent variables influence a single outcome. The regression analysis will show which independent variables (such as ethnicity, anxiety scores, duration of the desire to have children,...) have an influence on the score difference of IBS-SSS questionnaire. AIC will be used to evaluate the different possible models which will include different independent variables. The model with the lowest AIC will be used.

All analyses will be performed with SPSS.

11 Ethical Considerations

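### Lowest-AIC selection in section 10.5 can drop age, so the follicle-count (H11) and hormonal-profile (H10) associations with IBS-SSS change may be confounded

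*Protocol*

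**What the plan says.** Section 10.3 takes age from the patient file: "The following information will be gathered: age, the type of medication administered for ovarian stimulation", followed by the hormonal profile, the follicle number on the last ultrasound and the oocytes retrieved. Section 4 adds length and weight before stimulation. BMI is not named but can be derived.

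Section 10.5 describes two regressions.

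- **Logistic model, presence of IBS (yes/no).** "The independent variables include GAD-7 score, PHQ-9 score, ethnicity, duration of the desire to have children, the number of follicles found on the US", and the list then trails off. The selection rule is: "The model with the lowest AIC will be the final model".
- **Linear model, change in IBS-SSS.** "The regression analysis will show which independent variables (such as ethnicity, anxiety scores, duration of the desire to have children,...) have an influence". The rule is the same: "The model with the lowest AIC will be used".

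Age, weight and BMI appear in neither list of examples, and no covariate is fixed in either model. Follicle number is named only in the logistic list, and hormonal profile in neither. H10 and H11 (section 6.2.1) concern changes in IBS symptoms, so the change model is their natural home. Section 6.3 also describes comparisons in subgroups by hormonal profile and ultrasound response, with no adjustment stated.

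**The concern.** AIC rewards prediction of the outcome. It does not ask whether removing a variable shifts the coefficient of another variable. Those are different questions, and the second is the one that matters when a coefficient is read as an influence.

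If age is related both to ovarian response and to symptom change, leaving it out passes part of its effect to follicle count or hormone levels. H10 or H11 could then be declared significant because younger and older women report different symptom changes, with no contribution from follicles or hormones. Under the stated rule, age stays only if it earns its place on fit. At 60 women per group, a moderate confounder often will not.

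**Working it through.** The protocol gives no significance level, effect size or correlation for this analysis, so there is no figure of its own to reproduce. The sample size is 60 + 60 = 120 (section 4). Section 10.5 does not make clear whether the change model is fitted per group or pooled, so both n=60 and n=120 are shown. The correlations and the two-sided 5% test are assumptions.

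**1. Age left out.** Let r be the age-factor correlation and b the standardised age effect on symptom change, with no true effect of the factor. The factor's expected standardised coefficient is then r × b. By Fisher's z, the test statistic is centred near atanh(rb) × √(n-3).

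- Sizes 0.5 and 0.3: rb = 0.15. At n=60, 0.1511 × √57 = 1.14, and P(|Z| > 1.96) is about 21%. At n=120, 0.1511 × √117 = 1.63, giving about 37%. Simulation (4,000 runs) gave 21.6% and 37.4%.
- Sizes 0.5 and 0.2: rb = 0.10, about 12% at n=60.
- Sizes 0.6 and 0.3: rb = 0.18, about 28% at n=60.

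**2. When AIC drops age.** One added variable lowers AIC only if it improves n × ln(RSS) by more than 2, that is |t| above about √2 = 1.41. With r = 0.5, b = 0.2 and n=60, age's own statistic is centred near 0.2 × √(1-0.25) × √60 / √(1-0.04) = 1.37. The chance of falling short is about 51%; simulation gave 49.8%. The factor √(1-r²) means that a stronger link between age and the factor makes age easier to drop.

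**3. False-positive rate for a null factor.** The factor is always in the model and r has size 0.5:

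| n | size of b | AIC drops age | Age omitted | Age an AIC candidate | Age kept |
|---|---|---|---|---|---|
| 60 | 0.2 | 49.8% | 11.8% | 8.7% | 4.9% |
| 60 | 0.3 | 24.5% | 21.6% | 9.3% | 5.1% |
| 120 | 0.2 | 30.3% | 20.3% | 9.8% | 5.4% |
| 120 | 0.3 | 6.6% | 37.4% | 6.3% | 4.9% |

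A second design used follicle count, age and three noise variables, with all-subsets lowest AIC, r from -0.5 to -0.6 and b from -0.2 to -0.3. At n=60 it gave about 9-12% with age a candidate (dropped in 21-47% of runs), about 10-32% with age never offered, and about 5-6% with age kept. At n=120 with age a candidate, one set of runs gave 7-8% and another 7.5-9.6%.

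**4. How much is confounding.** With r = -0.5 and b = 0 there is nothing to confound. AIC selection among the candidates still gave about 7-8% at n=60, against about 5.5% with all candidates kept. So much of the 9-12% is testing after selection, and confounding adds a few percentage points. In the table's design at n=60, the null factor's mean coefficient was 0.10 to 0.15 with age omitted and about 0.01 to 0.02 with age a candidate.

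**5. Weaker links.** With r = 0.2 and b = 0.1, omission at n=60 gives 5.6%. With either link at zero there is no bias from omission (4.6-5.4%).

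**The case against.** The strongest reply is that nothing has been omitted. Both covariate lists are open-ended examples, section 10.3 collects age for this study, and a full list may sit in a statistical analysis plan that was not available. That disposes of any complaint that age is simply unnamed. It does not dispose of the selection rule, which the protocol does settle: lowest AIC decides. A later plan that kept age regardless would depart from section 10.5.

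Three stronger readings are tempting, and the documents do not support them.

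- **That the associations are confounded.** This needs age to be related to both the factor and symptom change, and the documents give neither relation. Section 5.1 mentions obesity in PCOS but says nothing of age and symptoms, or of BMI by phenotype or ethnic group.
- **That false positives run up to about a third at n=60, or half at n=120.** Such figures assume that age is never offered to the model. They fit an unadjusted comparison like the section 6.3 subgroups, not the AIC procedure in section 10.5.
- **That BMI should be forced into every model.** For ethnicity (H8) and PCOS phenotype (H9), BMI may lie on the pathway, and adjusting for it would then answer a different question.

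It is also fair to say that H10 and H11 are secondary hypotheses in a study that calls itself explorative, and that they are worded as differences or associations. That limits the consequence. But section 10.5 goes further when it speaks of influence, and that is the reading an unadjusted coefficient cannot carry.

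**Conclusion.** The point holds in a conditional form. Section 10.5 lets age leave the IBS-SSS-change model on fit alone while reading what remains as influential, so the H10 and H11 associations may be confounded by age. Under the assumed correlations, the cost of the AIC rule is modest: about 9-12% false positives at n=60 and about 7-8%, at times near 10%, at n=120, against 5-6% with age kept. Part of that is selection, not confounding. The cost is larger if age is never offered, and negligible if either link is weak. The simulations model age as the confounder of a single null factor standing for follicle count; applying them to hormone levels is by analogy. The primary before-after comparison is within woman, so fixed differences in age between women do not confound it.

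**What to change.** In section 10.5, state that age, as a continuous variable, stays in the IBS-SSS-change models used for H10 and H11 whatever its AIC, and that the factor of interest is tested on top of it. Replace the language of influence with association. For H8 and H9, report results with and without BMI (derived from length and weight) as a sensitivity analysis, and do not make BMI a required covariate.

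The data are already collected. The cost is a sentence or two and one degree of freedom per model, out of about 60 if the groups are fitted separately. It should be settled before the data are analysed, because adjustment added later would be post hoc. Keeping age does not cure testing after selection among the remaining candidates, which is a separate matter.

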11.1 Ethical Conduct of the Study

11.1.1 Declaration of Helsinki

The trial will be performed in accordance with the Declaration of Helsinki, the conditions and principles of Good Clinical Practice, the protocol and applicable local regulatory requirements and laws.

11.1.2 Ethics Committee

Before the start of the trial or implementation of any amendment, approval of the trial protocol and amendments, informed consent forms and other relevant documents will be obtained from the applicable ethical committee(s).

11.2 Recruitment and Informed Consent

Each participant shall provide a signed and dated Informed Consent Form before performance of any study-related activities. The IC form that is used will be approved by reviewing EC and will be in a language that the participant can read and understand. The ICF will be in accordance with current ICH and GCP guidelines and with applicable local regulations.

11.3 Study Data Protection

The collection and processing of personal data from participants enrolled in the study will be limited to those data that are necessary to fulfill the objectives of this study. These data must be collected and processed with adequate precautions to ensure confidentiality and compliance with applicable data protection laws and regulations.

11.4 Subject Identification

The participant identification will be treated as confidential and will be filed by the investigator in an identification log. This log is kept at the participating site and shall not be copied. In all reports and communication between the site and the Sponsor the participant shall be identified with a participant study number.

12 Insurance

VUB is, as Sponsor of the trial, responsible for ensuring appropriate general/product liability insurance and as required in accordance with applicable laws and regulations, country-specific liability insurance coverage for claims made by a trial subjects for injury arising from the subject's participation in the trial.

13 Reporting and Dissemination

The data and information collected during this trial will be reported in a publication in a scientific/medical journal. Reporting of trial results will be performed according to local regulations.

For the correct authorship rules we refer to the International Committee of Medical Journal Editors: <https://www.icmje.org/recommendations/browse/roles-and-responsibilities/defining-the-role-of-authors-and-contributors.html>

14 Finance and Conflict of Interest Statement

Investigators and study team members will provide the Sponsor with sufficient, accurate financial information in accordance with local regulations to allow the Sponsor to submit complete and accurate financial certification or disclosure statements to the appropriate regulatory authorities/ethics committee. Any update of information on financial interests should be disclosed during the course of the study.

15 References

APPENDIX 1: ROME IV IBS QUESTIONNAIRE (English version) (Rome Foundation)

Question

40. In the last 3 months, how often did you have pain anywhere in your abdomen?

Answer

- ① Never
- ① Less than one day a month
- ② One day a month
- ③ Two to three days a month
- ④ Once a week
- ⑤ Two to three days a week
- ⑥ Most days
- ⑦ Every day
- ⑧ Multiple times per day or all the time

40b. In the last 3 months, how often did you have discomfort anywhere in your abdomen ?

- ① Never → If you answered "Never" on question 40 and 40b: **Skip question 41**
- ① Less than one day a month
- ② One day a month
- ③ Two to three days a month
- ④ Once a week
- ⑤ Two to three days a week
- ⑥ Most days
- ⑦ Every day
- ⑧ Multiple times per day or all the time

41. How often did this pain in your abdomen happen close in time to a bowel movement -- just before, during, or soon after? (Percent of times with pain)

- ① 0% Never
- ① 10%
- ② 20%
- ③ 30%
- ④ 40%
- ⑤ 50%
- ⑥ 60%
- ⑦ 70%
- ⑧ 80%
- ⑨ 90%
- ⑩ 100% Always

42. How often did your stools become either softer than usual or harder than usual when you had this pain? (Percent of times with pain)

- ① 0% Never
- ① 10%
- ② 20%
- ③ 30%
- ④ 40%
- ⑤ 50%
- ⑥ 60%
- ⑦ 70%
- ⑧ 80%
- ⑨ 90%
- ⑩ 100% Always

43. How often did your stools become either more frequent than usual or less frequent than usual when you had this pain? (Percent of times with pain)

- ① 0% Never
- ① 10%
- ② 20%
- ③ 30%
- ④ 40%
- ⑤ 50%
- ⑥ 60%
- ⑦ 70%
- ⑧ 80%
- ⑨ 90%
- ⑩ 100% Always

48. Has it been 6 months or longer since you started having this pain?

- ① No
- ① Yes

Type 1		Separate hard lumps, like nuts
Type 2		Sausage-shaped but lumpy
Type 3		Like a sausage but with cracks on the surface
Type 4		Like a sausage or snake, smooth and soft
Type 5		Soft blobs with clear-cut edges
Type 6		Fluffy pieces with ragged edges, a mushy stool
Type 7		Watery, no solid pieces

Bowel movements of Type 1 or 2 and also of Type 6 or 7 in the picture above can be considered to be abnormal. Type 1 or 2 means you are constipated, and Type 6 or 7 means you have diarrhea.

64. In the last 3 months, when you had abnormal stools, what were they usually like?

- ① Usually constipation (like Type 1 or 2 in the picture)
- ② Usually diarrhea (like Type 6 or 7)
- ③ Both diarrhea and constipation - that is, more than 1/4 of all the abnormal bowel movements were constipation and more than 1/4 were diarrhea
- ④ Not applicable, because I never or rarely had abnormal bowel movements

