9.3 Assessment types

9.3.1 IBS symptoms

The IBS-SSS (IBS Symptom Severity Scale) (appendix 2) and Rome IV Criteria (appendix 1) are used to determine IBS symptoms. The result of the IBS-SSS is a score of 0 to 500. Each of the five topics is rated from 0 to 100. The topics are number of days with abdominal pain, satisfaction with bowel habits, abdominal pain, bloating/distention and IBS-related quality of life. A 15% change in the score

is considered clinically significant. (29) A score of 75-175 is considered mild, a score of 175 to 300 is considered moderate and a score of >300 is considered severe. (30) The Rome IV Criteria for IBS describe recurrent abdominal pain on average at least 1 day per week in the last 3 months, associated with two or more of the following criteria: associated with a change in the frequency of stool, associated with a change in the form of stool and/or related to defecation. The criteria should be present for the last 3 months and symptoms should be present at least 6 months before the diagnosis is made. (16)

IBS prevalence differs greatly based on if the Rome IV or Rome III criteria are used. The Rome Foundation Global study reported an overall prevalence of 3,8% when the Rome IV criteria are used and an overall prevalence of 10,1% when the Rome III criteria are used. (15) The Rome IV criteria ask for abdominal pain while the Rome III criteria ask for abdominal discomfort (an uncomfortable sensation and not necessary pain). (16) Because of this big difference in prevalence, this study will first ask for abdominal pain (Rome IV criteria) and afterwards ask for abdominal discomfort (Rome III Criteria). This gives us a more complete picture of the IBS symptoms.

9.3.2 *Gastrointestinal symptoms*

The Gastrointestinal Symptom Rating Scale (appendix 3) contains 15 questions divided over five domains: abdominal pain, reflux syndrome, indigestion syndrome, constipation syndrome and diarrhea syndrome. Each question is scored from 1-7 depending on the inconvenience that the person experienced in the previous week. A higher score correlates with more inconvenient symptoms. (31) This questionnaire is used to get a more general overview of gastrointestinal symptoms.

9.3.3 *Depression levels*

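### Appendix 1 asks about discomfort only in item 40b; the items that decide IBS status ask about pain, so Rome III status is not validly measured in women with discomfort but no pain

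*Protocol*

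**What the plan says.** Section 9.3.1 of the protocol gives the reason for using two definitions: cited prevalence differs greatly between Rome III and Rome IV. It therefore announces that "this study will first ask for abdominal pain (Rome IV criteria) and afterwards ask for abdominal discomfort (Rome III Criteria"). Section 5.6 describes discomfort as an unpleasant sensation that need not be pain, and says Rome III asks for it in addition to pain. Both definitions appear in primary objective 1 (section 6.1), in H1 (section 6.1.1) and in the binary outcome of section 10.5. Sections 9.2.2 and 9.2.3 name only the Rome IV form (Appendix 1) for the two visits.

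Appendix 1 carries this out by adding one item: "40b. In the last 3 months, how often did you have discomfort anywhere in your abdomen". The routing reads "If you answered 'Never' on question 40 and 40b: Skip question 41". The items that follow are:

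- relation to defecation: "41. How often did this pain in your abdomen happen close in time to a bowel movement";
- stool form: "42. How often did your stools become either softer than usual or harder than usual when you had this pain";
- stool frequency: "43. How often did your stools become either more frequent than usual or less frequent than usual when you had this pain";
- onset: "48. Has it been 6 months or longer since you started having this pain".

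Items 41 to 43 are answered on a scale headed "Percent of times with pain". No other Rome III items appear in the protocol.

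**The concern.** Rome III was added to pick up women whose complaint is discomfort rather than pain. For those women the form records how often the discomfort occurs and nothing else. Whether it is linked to defecation, goes with a change in stool form or frequency, or began at least six months ago is never asked. The routing was adapted to let discomfort-only women through, but the questions they are let through to were not.

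The Rome III part of the primary prevalence outcome would then depend on how each woman handles questions that do not apply to her. She may also handle them differently before stimulation and on the day of pick-up.

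**Working it through.** **Step 1: what a classification needs.** Section 9.3.1 sets out, for Rome IV, recurrent pain with at least two of three associated features, present for three months, with onset at least six months before diagnosis. The protocol gives no separate feature list for Rome III. Whatever the exact Rome III rule, if it uses these features it needs them asked about discomfort.

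**Step 2: what the form yields for each answer pattern.** The Rome III column takes from section 5.6 that discomfort is additional to pain, so that a Rome IV-positive woman also meets Rome III.

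| Item 40 (pain) | Item 40b (discomfort) | Rome IV | Rome III |
|---|---|---|---|
| Never | Never | negative | negative, whatever is entered at 42, 43 and 48 |
| Present | Never | from 41–43 and 48 | from the same pain items |
| Present | Present | from 41–43 and 48 | positive if Rome IV positive; otherwise unknown, because the features of the discomfort were not asked |
| Never | Present | negative | unknown |

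**Step 3: the last row.** The skip needs Never on both 40 and 40b, so this woman goes on to 41. The denominator of the scale for 41 to 43, the times with pain, is empty for her. A 0% may mean that she has no pain, or that her discomfort is unrelated to bowel movements. A blank may mean not applicable or overlooked. A non-zero percentage suggests that she read pain as discomfort, or that her answer to item 40 was wrong. A literal reader enters 0% and No, and would count as negative under any rule that uses these items.

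**Step 4: scale, as illustration only.** There is no stated power or sample size calculation to reproduce. Inputs: Rome III 10.1% and Rome IV 3.8% (sections 5.6 and 9.3.1); 60 + 60 = 120 women (section 4).

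- Gap: 10.1 − 3.8 = 6.3 percentage points.
- Share of Rome III cases that are not Rome IV positive: 6.3 / 10.1 = 62%, taking every Rome IV case to be a Rome III case.
- Expected counts in 120: Rome III 120 × 0.101 = 12.1; Rome IV 120 × 0.038 = 4.6; gap 120 × 0.063 = 7.6 (60 × 0.063 = 3.8 per group).
- If the whole gap were discomfort-only women, measured Rome III prevalence would be 10.1% with none missed, 10.1 − 0.5 × 6.3 = 7.0% with half missed, and 3.8% with all missed.

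The protocol does not give the discomfort-only share, so these figures show a range under an assumption.

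**The case against.** The strongest reply is that the authors clearly meant item 41 to cover discomfort, since the routing sends discomfort-only women there, and that some women will read it so. That is fair. A reader might infer that every such woman will be scored Rome III negative. The protocol does not support this: it states no Rome III scoring rule and cannot say how women will read the items. What stands is that the form separates pain from discomfort in 40 and 40b and then asks about pain, so a literal answer is a reasonable one.

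A scoring rule may sit in an analysis plan that is not shown. Its absence from the protocol is not the point: no rule can recover answers that were never asked for.

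H1 concerns change, and the same form is used at both visits. This also stands in part, because the size and direction of any bias in the before-after difference cannot be determined from the protocol. The criteria also look back three months and require onset at least six months earlier. Discomfort that begins during stimulation would fail the onset item even if it were reworded, so correcting the wording gives a valid status at each visit without making that status responsive to one treatment cycle.

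The skip instruction names only question 41, so women with neither symptom still meet 42, 43 and 48. A reader might count this as a further source of error. It changes no classification, because those women are negative on both definitions.

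The study is explorative, and section 9.3.1 presents the discomfort question as giving a fuller picture. Rome III is nevertheless written into the primary objective and H1.

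**Conclusion.** The point holds for a limited group: women who report discomfort on 40b and are not Rome IV positive, above all those with no pain. Their Rome III status is not validly measured, and under-counting is likely if they answer literally. Rome IV status and the IBS-SSS hypothesis (H2) are untouched.

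Two stronger readings should be resisted.

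- The 3.8 women per group, or 7.6 of 120, might be taken as an upper limit. They are not. The 10.1% and 3.8% are overall figures from a global study. Section 5.6 reports prevalence up to threefold higher in women than in men and a doubled risk in PCOS, and section 5.9 cites 7.9% to 49.3% across studies. Nor are they estimates, since not Rome IV positive is not the same as discomfort only.
- It might seem that forms completed so far are worthless for Rome III. On the description in section 5.6, Rome IV-positive women and women with neither symptom remain classifiable.

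The conclusion rests on the English form. The Dutch and French wording is not shown and should be checked.

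**What to change.** Leave items 40 to 43 and 48 as they are, so that Rome IV measurement is preserved. Rewording them to cover pain or discomfort together would put the sound half at risk. Add a parallel set of 41, 42, 43 and 48, worded for *this discomfort* and asked of every woman who reports any discomfort on 40b, at both visits and in all three languages. As tidying, extend the skip to all dependent items. Record the form version for each questionnaire.

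On forms completed before the change, treat Rome III status as indeterminate only for women who report discomfort on 40b and are not Rome IV positive.

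If the form is not changed, remove Rome III from H1 and report 40b descriptively.

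The cost is about four extra short items, an amendment to the ethics committee, and the loss of a usable before-after Rome III pair for some women already enrolled. Section 7.2 plans inclusions from December 2025 to July 2026, so that loss grows with delay.
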